NCT 04471805 Study Title: 4 mA tDCS, Estrogen, and Leg Muscle Fatigability

This study employed a double-blind, randomized, crossover design, wherein all subjects received both active and sham stimulation during each phase of their menstrual cycle. Each of the 10 subjects completed a total of 6 visits to the lab. The first visit was a familiarization visit where maximal strength testing was performed to confirm leg dominance, and an isokinetic fatigue task (FT) was completed to familiarize each subject with the FT performed during the evaluation sessions. Additionally, subjects were asked about the start of their previous menstrual cycle, along with the projected start of their next menstrual cycle. The start of the menstrual cycle was deemed the first day of menstruation. Sessions were then scheduled to correspond with high and low points of estrogen level throughout the cycle. The early follicular phase (days 3–4) was targeted for low estrogen levels. The late follicular phase (days 9–10) and mid-luteal phase (days 18–20) were targeted for high estrogen levels. Sessions were scheduled so that each subject had both active (4 mA) and sham tDCS during each phase (early follicular, late follicular, and mid-luteal) of their menstrual cycle to fully assess the effects of stimulation. Due to the diurnal nature of estrogen, visits 2–6 were scheduled at the same time of day for each individual subject (i.e., ± 2 h for each session). Testing sessions began with a blood draw and assay to assess serum estrogen levels, followed by tDCS administration (active or sham), and right and left leg FTs.

Strength testing was performed on a HUMAC NORM isokinetic dynamometer (CSMi, Stoughton, MA, USA). Before beginning the strength testing, subjects completed a warm-up exercise which consisted of 15 repetitions of knee extension and knee flexion (60°/s, concentric/concentric). After resting for ≥ 30 s, three repetitions of maximal strength isometric knee extension and flexion were completed at 65° and 30°, respectively, with ≥ 30 s of rest between each repetition. Then, five repetitions of maximal strength isokinetic knee extension and flexion were completed at 60°/s (concentric/concentric) with ≥ 30 s of rest between each set. The right leg was always tested first, followed by the left. Strong verbal encouragement was provided during each repetition to ensure maximal effort from the participants. The greatest torque value acquired during either of the strength testing tasks (isometric or isokinetic) was utilized to objectively confirm right-side dominance. Strength testing was performed on a HUMAC NORM isokinetic dynamometer (CSMi, Stoughton, MA, USA). Before beginning the strength testing, subjects completed a warm-up exercise which consisted of 15 repetitions of knee extension and knee flexion (60°/s, concentric/concentric). After resting for ≥ 30 s, three repetitions of maximal strength isometric knee extension and flexion were completed at 65° and 30°, respectively, with ≥ 30 s of rest between each repetition. Then, five repetitions of maximal strength isokinetic knee extension and flexion were completed at 60°/s (concentric/concentric) with ≥ 30 s of rest between each set. The right leg was always tested first, followed by the left. Strong verbal encouragement was provided during each repetition to ensure maximal effort from the participants. The greatest torque value acquired during either of the strength testing tasks (isometric or isokinetic) was utilized to objectively confirm right-side dominance.

The isokinetic fatigue task (FT) comprised 40 consecutive repetitions of maximal effort isokinetic knee extension and flexion (120°/s, concentric/concentric). In visits 2–5, a 15-repetition warm-up exercise was completed before the FT, as detailed above. The FT was performed on the dominant (right) leg first and ≥ 5 min rest was provided to allow for adequate heart rate and respiratory recovery before starting the left leg FT. Vigorous verbal encouragement and visual feedback (i.e., per rep work bars) were given to ensure the participants were performing maximal effort contractions throughout the fatigue tasks. The largest torque from each repetition was included in the analysis.

Muscle activity throughout the strength and fatigue tasks was recorded via a wireless EMG system (Ultium-EMG, Noraxon, USA Inc., Scottsdale, AZ, USA). EMG electrodes (3M Red Dot Monitoring Electrode, Model 2560; 3M Corp., St. Paul, MN, USA; 2 cm between each 1.3 cm effective area) were secured bilaterally over the rectus femoris, vastus medialis, vastus lateralis, and semitendinosus corresponding to a 3D muscle map which followed SENIAM guidelines and was provided by the EMG software (MR 3.14, myoMUSCLE, Noraxon USA Inc., Scottsdale, AZ, USA). To increase electrode placement consistency, the same researchers placed the electrodes on the subjects during each visit. The electrode sites were prepared by shaving and cleaning the electrode site with an alcohol wipe before placing the electrodes. The electrodes and wireless transmitters

were secured in place with elastic bandages and EMG data were collected at 2000 Hz.

Sessions 2–6 began with a blood draw in the Clinical Research Unit at the University of Iowa Hospital and Clinics (UIHC). Staff nurses collected 4.5 mL blood from the median cubital vein of the left arm (total volume collected per subject = 9 mL) for the estrogen assay. Samples were immediately analyzed for serum estrogen levels after the blood draws by UIHC Pathology technicians using an Electrochemiluminescence Assay (Roche Diagnostics, Basel, Switzerland).

Statistical Analysis Plan

A stimulation condition (active vs. sham) by estrogen level (high vs. low) repeated measures ANOVA was performed on the FI values and EMG activity for the right and left extensors and flexors. Post hoc analyses (paired t-tests and Bonferroni correction) and effect size (Cohen's d) were calculated to clarify significant main effects and interactions. Significance was accepted at $p \leq 0.05$. Normality and sphericity assumptions were evaluated with the Shapiro–Wilk test and Mauchly's test of sphericity for the ANOVAs. Greenhouse–Geisser corrections were used when the sphericity assumption was violated. GraphPad Prism 9 (GraphPad Software, San Diego, CA, USA) was utilized to perform the analyses.

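### The stated number of evaluation sessions is contradictory, and the planned ANOVA has no session term while starting phase and active/sham order are undescribed, so a session trend could bias the estrogen main effect if nearly all subjects started in the same phase

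*Combined protocol and SAP*

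**What the plan says.** The analysis is a two-factor within-subject model: "A stimulation condition (active vs. sham) by estrogen level (high vs. low) repeated measures ANOVA was performed". The Statistical Analysis Plan adds post hoc tests and assumption checks, but no session, period or sequence term and no check for order effects.

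The study design paragraph says "This study employed a double-blind, randomized, crossover design" and does not state what was randomized. On timing it says "Sessions were then scheduled to correspond with high and low points of estrogen level throughout the cycle", with the early follicular phase as low estrogen and the late follicular and mid-luteal phases as high. It names no starting phase, no balancing of starting phase and no rule for active/sham order.

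On the number of sessions:
- "Sessions were scheduled so that each subject had both active (4 mA) and sham tDCS during each phase" (study design paragraph).
- "Each of the 10 subjects completed a total of 6 visits to the lab", the first being familiarization (same paragraph).
- "Sessions 2–6 began with a blood draw" (blood draw paragraph), at 4.5 mL per draw, yet "total volume collected per subject = 9 mL".
- "In visits 2–5, a 15-repetition warm-up exercise was completed before the FT, as detailed above" (fatigue task paragraph).

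**The concern.** Each subject repeats an effort-dependent task of 40 maximal repetitions per leg over several visits. Performance may drift with practice or accumulated fatigue. Stimulation can be randomized within a phase, but estrogen level cannot: once a subject has started, the calendar fixes the order of low and high sessions. If almost everyone enters at the same phase, high-estrogen sessions fall systematically later (or earlier) than low ones, and the planned ANOVA would count part of a drift as an estrogen effect.

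The contradictory session count makes this harder to judge. The layout determines which sessions each cell of the 2x2 averages, and therefore whether there is any order bias, in which direction and how large.

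**Working it through.** The plan states no sample-size, power or effect-size figure, so there is nothing of its own to reproduce.

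**Session count.** Two conditions × three phases = 6 evaluation sessions. Visits 2–6 = 5. Blood: 9 / 4.5 = 2 draws, whereas 5 × 4.5 = 22.5 mL.

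**Inputs.** From the documents: 10 subjects, early follicular (E) low, late follicular (L) and mid-luteal (M) high, significance at 0.05. Assumed: two-sided test, within-subject SD of 1, no true estrogen effect, phase determines high or low, the two high phases are averaged, stimulation order random within phase, and linear drift b of 0.1, 0.2 or 0.3 SD per session.

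**Offset of the high-minus-low contrast = b × (mean position of high sessions − mean position of low sessions).**

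Six sessions over two cycles:
- E start (E,L,M,E,L,M): low at 1, 4 (mean 2.5), high at 2, 3, 5, 6 (mean 4), so +1.5b.
- L start: low at 3, 6 (mean 4.5), high at 1, 2, 4, 5 (mean 3), so −1.5b.
- M start: low at 2, 5, high at 1, 3, 4, 6, both means 3.5, so 0.

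Five sessions:
- E start (E,L,M,E,L): low mean 2.5. The single M session shares a condition with the first or the second L session. The high cells are then positions (2, 3) and 5, averaging (2.5 + 5)/2 = 3.75, offset +1.25b; or (3, 5) and 2, averaging (4 + 2)/2 = 3, offset +0.5b. The mean is +0.875b, and the offset varies between subjects with variance 0.375²b² = 0.141b².
- M start: the mirror image, −0.875b.
- L start: only one low session, so one cell of the 2x2 is empty for that subject.

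**Variance of one subject's contrast.** Six sessions: 1/2 + 1/4 = 0.75. Five sessions: low 0.5, high 0.25 + 0.125, total 0.875, plus 0.141b².

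**False-positive rate.** The estrogen main effect is a one-sample t-test on 10 contrasts (9 df), with noncentrality = offset / √(variance/10).

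| All start early follicular | b = 0.1 | b = 0.2 | b = 0.3 |
|---|---|---|---|
| Five sessions: noncentrality | 0.30 | 0.59 | 0.88 |
| Five sessions: rate | 5.8% | 8.3% | 12.4% |
| Six over two cycles: noncentrality | 0.55 | 1.10 | 1.64 |
| Six over two cycles: rate | 7.8% | 16.6% | 31.2% |

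The five-session rates are approximate because the offset varies with stimulation order; simulation agrees with them.

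**Mixed starts.** Five sessions, 8 E and 2 M: mean offset (8 × 0.875 − 2 × 0.875)b/10 = 0.525b; simulated rates about 5%, 6% and 7%. Six sessions, 8 E, 1 L and 1 M: 6.3%, 9.8% and 15.2%. Six sessions, 4/3/3: bias at most about 0.04 SD, with rates not above nominal beyond simulation error.

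**Stimulation contrast, order independent by phase.** There is no bias. The variance is 0.875 + 3.531b² with five sessions (+4%, +16%, +36%) and 0.75 + 3.375b² with six over two cycles (+4.5%, +18%, +40.5%).

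**The case against.** The strongest reply is that both conditions for bias are assumed. No document reports a drift, and visit 1 includes the full fatigue task, which may use up much of any practice effect. The cycle-day windows put successive phases at least 5 days apart, so accumulating fatigue is less plausible. A drift of 0.3 SD per session without plateau amounts to 4 × 0.3 = 1.2 SD over five sessions, which is large. Nor does any document say that starts were concentrated. All of this stands, and it is why the rates are a range under stated assumptions and not an estimate for this trial.

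Several stronger readings are tempting and unsupported:
- A reader might infer that bias follows whenever most subjects share a starting phase. With five sessions, an 8/2 split leaves the rate near nominal; the start must be nearly universal.
- A reader might take 31% as the expected error rate. It needs six evaluation sessions, hence seven visits with familiarization, against six stated, as well as the largest assumed drift and a universal start.
- A reader might take the warm-up sentence as a statement of four evaluation sessions. It says only at which visits a warm-up was done.
- A reader might infer that the stimulation comparison is biased. If order varied independently by phase, it loses only precision.

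It is also fair to say that the session count is a documentation defect distinct from the modelling point. The two are linked only because the layout determines the offset.

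**Conclusion.** The session count is contradictory on the face of the text, and the passages must be reconciled. The missing session term, with starting phase and active/sham order undescribed, is a conditional weakness of the estrogen main effect. It matters if there is a session trend and if nearly all subjects started in the same phase: early follicular or mid-luteal with five sessions, early or late follicular with six over two cycles. In the five-session layout that the visit numbering implies, the inflation is modest even with a universal start. It rests on the assumed drift, on linearity and on phase defining estrogen level; the plan does not say whether phase or the assay assigned high and low. The documents do not show that the estrogen result is biased. They do not give a reader the means to rule it out.

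**What to change.** 1. Reconcile the number of evaluation sessions and the blood-volume figure.
2. Report starting phase and stimulation condition by visit for each subject. If starts were balanced, or all mid-luteal with six sessions over two cycles, say so; the session term then serves precision only.
3. Beside the planned ANOVA, show a session-level sensitivity model with stimulation, estrogen level, their interaction and session number as a linear 1-df term. Name one error method in advance: cluster-robust errors by subject (CR2) with Satterthwaite df. In simulation with a common start and linear drift this held the rate at 4.4–5.4%. Label it post hoc if results are already known.

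Two variants should be avoided. A categorical session term makes estrogen non-estimable under a common start. A random intercept alone rejects about 9% with five or six sessions and no drift when the estrogen effect varies between subjects (SD 0.75, assumed).

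The cost is a change of wording and a re-fit on data that should already be held, possibly in other software, plus 1 df. With a common early follicular start the estrogen standard error widens by about 4% (five sessions, ratio 1.044) or 10% (six over two cycles, ratio 1.099). Protection against a one-off first-session shift is only partial: for a 1.0 SD shift, false positives fall from 33% to 19% with five sessions and from 38% to 18% with six. The model should therefore stand as a sensitivity analysis and not replace the planned ANOVA.

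### Post hoc paired t-tests use single-step Bonferroni. Holm's step-down gives the same familywise control, never rejects less, and could recover a second real simple effect at n = 10 (minor, cheap improvement)

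*Combined protocol and SAP*

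**What the plan says.** The Statistical Analysis Plan specifies "A stimulation condition (active vs. sham) by estrogen level (high vs. low) repeated measures ANOVA", which "was performed on the FI values and EMG activity for the right and left extensors and flexors". The follow-up is "Post hoc analyses (paired t-tests and Bonferroni correction", together with Cohen's d, and these "were calculated to clarify significant main effects and interactions". The significance level is 0.05; sidedness is not stated.

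The design paragraph that opens the document describes a "double-blind, randomized, crossover design, wherein all subjects received both active and sham stimulation", and reports that "Each of the 10 subjects completed a total of 6 visits to the lab". The post hoc contrasts are therefore within-subject, with 9 degrees of freedom.

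The documents do not give the number of comparisons in the Bonferroni family, a planned effect size, a power figure, a reason for preferring Bonferroni, or any plan for simultaneous confidence intervals.

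**The concern.** The 2x2 analysis asks whether tDCS acts at high estrogen, at low estrogen, or at both. After a significant interaction, the answer rests on the post hoc paired tests. Single-step Bonferroni holds every test to the strictest threshold, even after another contrast in the family has been rejected. Holm relaxes the threshold at each rejection, at no cost in familywise error.

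The loss falls on the second effect. Where tDCS acts at both estrogen levels, Bonferroni is more likely than Holm to report an effect at one level only. With 10 subjects there is little power to spare.

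**Working it through.** **Inputs.** From the documents: n = 10, paired contrasts, alpha 0.05, two levels per factor. Assumed, because the documents are silent: two-sided tests; family size m = 2 (tDCS at each estrogen level), 4 (all simple effects) or 6 (all cell pairs); normal data; correlation 0.5 between cells; standardised paired difference dz = mean difference / SD of the differences. The plan states no power or adjusted alpha, so there is no figure of its own to reproduce.

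**Step 1: validity of Bonferroni.** For independent tests the familywise error is 1 - (1 - 0.05/m)^m, which is 0.0494 (m = 2), 0.0491 (m = 4) and 0.0490 (m = 6). Simulated under the full null with correlation 0.5, it is 0.050, 0.047 and 0.044, the same for Holm.

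**Step 2: why Holm never rejects less.** Order the p-values p(1) ≤ ... ≤ p(m). Bonferroni rejects when p(j) ≤ 0.05/m. Holm works upward, rejecting while p(j) ≤ 0.05/(m - j + 1).
- m = 2: Bonferroni 0.025, 0.025; Holm 0.025, 0.05.
- m = 4: Bonferroni 0.0125 four times; Holm 0.0125, 0.0167, 0.025, 0.05.

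No Holm threshold is below 0.05/m, so every Bonferroni rejection is kept. When Holm reaches its first true null, all the true nulls (m0 of them) are still in play, so the threshold is at most 0.05/m0. The Bonferroni inequality then bounds the error at 0.05 under any dependence. The first thresholds coincide, so the chance of at least one rejection is identical.

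**Step 3: where the choice cannot matter.** A main effect with two levels is a single comparison (m = 1), and both methods use 0.05. The choice matters mainly after a significant interaction.

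**Step 4: size of the gain.** The figures below are simulated at n = 10, among runs with a significant interaction.

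| True pattern | m | Outcome | Bonferroni | Holm | Gain (points) |
|---|---|---|---|---|---|
| Opposite-sign tDCS effects, dz 1.0 each, fully symmetric crossover | 4 | both tDCS effects declared | 31% | 54% | 23 |
| Same | 2 | both declared | 48% | 65% | 17 |
| Opposite-sign, dz 1.0 each, equal sham cells | 4 | both declared | 31% | 47% | 16 |
| Same-sign, dz 1.5 and 0.5 | 4 | both declared | 5.6% | 9.3% | 3.7 |
| Same | 2 | both declared | 9.8% | 16.7% | 6.9 |
| Only the active/high-estrogen cell differs, dz 1.0 | 4 | that effect found | 76% | 80% | 4 |
| Same | 2 | that effect found | 87.4% | 87.7% | 0.3 |

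In the third row the Bonferroni figure carries over from the first: it depends only on the two tDCS contrasts and the interaction, which a sham difference does not alter.

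These percentages are conditional. With only one cell differing, the interaction is significant in about 52% of runs. Counted over all runs, the m = 4 figures are then about 39% and 41%. The same-sign pattern has the same interaction size (1.5 - 0.5 = 1.0), so over all runs its gains are about 0.52 × 3.7 = 1.9 and 0.52 × 6.9 = 3.6 points.

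**Step 5: a further refinement after a significant interaction.** Write A and S for active and sham, H and L for high and low estrogen. Then (AH - SH) - (AL - SL) = (AH - AL) - (SH - SL) = the interaction. If it is non-zero, each of these two pairs contains at most one true null, so at most 2 of the 4 simple effects are null. This justifies Shaffer divisors 2, 2, 2, 1 in place of Holm's 4, 3, 2, 1. With one cell differing (dz 1.0, m = 4) they raise the conditional figure from 80% to 87%. With the interaction gate, familywise error was 0.028 under the global null (Holm 0.018) and about 0.044 with one cell differing at dz = 2 (both methods). Without the gate, the restricted version reached 0.089 under the global null, so the gate is essential.

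**The case against.** The strongest reply is that nothing in the plan is wrong. Bonferroni is valid and cannot inflate false positives; a uniformly more powerful alternative makes it a less efficient choice, not an error. That stands, and it sets the severity.

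The scenario matters too. The largest gain, 31% to 54%, needs effects that reverse sign between estrogen levels and an estrogen shift in the sham condition in the opposite direction, so that all four simple effects are non-null. The documents suggest no such reversal. In the same-sign case Holm still misses the second effect in over 80% of the runs with a significant interaction (100 - 16.7 = 83.3% with m = 2). The main limit is n = 10: the dz needed for 80% power on one contrast is 1.00 unadjusted, 1.14 at m = 2, 1.28 at m = 4 and 1.37 at m = 6. Family size also matters: with one real effect, plain Bonferroni on two contrasts reaches 87.4%, about what the Shaffer divisors achieve with four. All of this stands, and it limits the gain without removing it.

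A reader might infer three stronger claims that the documents do not support:
- That the plan divides alpha by 4 or 6. No number of comparisons is stated, and the tDCS question needs only two contrasts.
- That real tDCS effects are being missed. No effect size, SD or result is given, and where Bonferroni rejects nothing, neither does Holm.
- That Bonferroni brings no benefit. It gives simple simultaneous intervals, although this SAP plans none.

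Finally, the text is in the past tense and reads as an analysis already done. Moving to a more permissive correction after seeing results would be data-dependent. That stands as a condition on the fix.

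**Conclusion.** The point holds as a cheap improvement of minor severity. Holm's advantage as a method, meaning equal familywise control and no lost rejection, is a mathematical fact that needs no assumption about effects. Its practical size does depend on assumptions: n = 10 from the documents, and assumed family size, dz, correlation 0.5, normality and two-sided testing.

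On those assumptions the gain is nil for main effects and about 0.3 points when one of two tDCS contrasts is real. For declaring both tDCS effects after a significant interaction, it is about 4 to 7 points with same-sign effects of dz 1.5 and 0.5, and about 17 to 23 points with symmetric opposite-sign effects of dz 1.0. The top of that range is close to a best case. No missed effect can be shown from the documents.

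**What to change.** In the Statistical Analysis Plan, replace *Bonferroni correction* with *Holm step-down correction* for the post hoc paired t-tests, and take that decision without regard to the results. If results are already known, the record should say when and on what grounds the choice was made.

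Optionally, for the four simple effects tested after a significant interaction, and only there, specify Shaffer divisors 2, 2, 2, 1.

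The cost is one phrase and a re-ordering of p-values already computed, with no new data or visits. The downside is that simultaneous confidence intervals matching Holm are less simple than Bonferroni's; the SAP plans none.

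### Cohen's d from paired contrasts in 10 subjects, with no small-sample correction named, is about 4% to 9% too large on average; report Hedges' g with a stated denominator

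*Combined protocol and SAP*

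**What the plan says.** The opening design paragraph describes a "double-blind, randomized, crossover design, wherein all subjects received both active and sham stimulation", and reports that "Each of the 10 subjects completed a total of 6 visits to the lab". Comparisons of active with sham, and of high with low estrogen, are therefore made within subject.

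The Statistical Analysis Plan specifies a two-factor repeated measures ANOVA "on the FI values and EMG activity for the right and left extensors and flexors". It follows this with "Post hoc analyses (paired t-tests and Bonferroni correction") and with effect sizes: "effect size (Cohen's d) were calculated". Both "were calculated to clarify significant main effects and interactions".

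That is all the document says about effect size. It does not state which SD divides the mean difference, whether a small-sample correction is applied, or whether an interval accompanies the estimate. It gives no expected effect, outcome SD or within-subject correlation.

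**The concern.** Cohen's d divides a mean difference by an estimated SD. In small samples the reciprocal of the estimated SD is too large on average, so d overstates the true standardised effect even when the mean difference is unbiased. With 10 pairs this is large enough to show in the reported figure, and the usual correction (Hedges' g) is not mentioned.

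Cohen's d is the only effect-size measure the plan names, so it is the figure a reader would carry forward. As an illustration (the document mentions no later trial), a crossover sized on an SD-of-differences d that is 9.4% too high would need about 1.0942² = 1.197 times the planned number, or 20% more subjects.

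There is a second, separate gap. For paired data, d can be taken from the paired t statistic or from the condition SDs, and the two answer different questions. The plan leaves this open.

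**Working it through.** **Inputs.** From the document: n = 10 subjects and paired contrasts, so n − 1 = 9 df. This assumes one value per subject per condition and no missing values. Not in the document: the within-subject correlation r, for which I assume 0 to 0.95. The calculations also assume normal data and equal SDs in the two conditions. The document gives no effect-size or power figure, so there is nothing to reproduce first.

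**1. Bias when d uses the SD of the differences (d_z = t/√n).** The expected value of d_z is the true value divided by

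J(m) = Γ(m/2) / [√(m/2) · Γ((m−1)/2)], approximately 1 − 3/(4m − 1).

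With m = 9, J = 0.9139 (approximation 1 − 3/35 = 0.9143) and 1/J = 1.094. Uncorrected d_z is 9.4% too large on average, whatever r is. Simulation with n = 10 gave ratios of 1.093 to 1.097.

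**2. Bias when d uses the average condition SD (d_av).** The two sample variances come from the same subjects and are correlated. Matching the variance of their average to that of a scaled chi-square gives effective df = 2(n − 1)/(1 + r²) = 18/(1 + r²).

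| assumed r | effective df | J | 1/J | simulated ratio |
|---|---|---|---|---|
| 0 | 18.0 | 0.958 | 1.044 | 1.043 |
| 0.5 | 14.4 | 0.947 | 1.056 | 1.057 |
| 0.8 | 10.98 | 0.930 | 1.076 | 1.073 |
| 0.95 | 9.46 | 0.918 | 1.089 | 1.088 |

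The simulation used n = 10, a true d_av of 0.5 and 400,000 replicates per r. The bias runs from about 4% to about 9%. Using 18 df is right only at r = 0. Applying J(9) to d_av would over-correct: at r = 0.5, 0.9139 × 1.056 = 0.965, about 3.5% too low.

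**3. Ratio of the two measures.** With equal SDs, d_z/d_av = 1/√(2(1 − r)).

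| assumed r | 0 | 0.25 | 0.5 | 0.7 | 0.8 | 0.875 | 0.9 | 0.95 |
|---|---|---|---|---|---|---|---|---|
| d_z/d_av | 0.71 | 0.82 | 1.00 | 1.29 | 1.58 | 2.00 | 2.24 | 3.16 |

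The ratio is below 1 for r < 0.5 and exceeds 2 only for r > 0.875.

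**4. Does correcting cost precision?** At n = 10 and an assumed true d_z of 0.5, simulation gives an uncorrected mean of 0.547 (bias about 0.05), a sampling SD of 0.39 and a root mean squared error of 0.391. Multiplying by J(9) lowers the root mean squared error to 0.355, so the correction removes the bias and also reduces total error.

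**The case against.** The strongest reply is that much of this rests on silence. The plan does not say that d was computed as t/√n, and does not say in so many words that no correction was applied. That is fair for the denominator. For the correction it carries less weight: the plan names Cohen's d, the corrected statistic is normally called Hedges' g, and the uncorrected value is biased upward under either denominator.

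A reader might go further and infer that the paired denominator more than doubles the effect, or that bias and denominator together inflate it about 1.7-fold at r = 0.8 (1.094 × 1.581 = 1.73). The document does not support this. It does not say that the SD of differences was used, and it gives no r. Doubling needs r above 0.875, and below 0.5 the SD of differences gives the smaller value. Nor is d_z an inflated d_av: it standardises by the spread of within-subject change, which is a legitimate choice in a crossover and the relevant one for sizing another crossover. The 1.7-fold figure multiplies an estimation bias by a change of definition.

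A reader might also infer that values will not be comparable across FI and EMG outcomes. That would follow, relative to between-woman variation, only if d_z were used and r differed between outcomes. The 9.4% factor is the same for every outcome with 9 df.

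It can also be said that the bias is small beside the sampling error (0.05 against 0.39 in the example) and is not the largest distortion. The plan ties d to significant effects. At an assumed two-sided 0.05 level, a contrast in 10 subjects is significant only when |d_z| reaches 2.262/√10 = 0.72. Among significant contrasts with a true d_z of 0.5, the mean reported d_z is about 1.0 in simulation. This stands: Hedges' correction does not remove that selection effect. It limits what the fix achieves but is no reason to leave a known bias in place.

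**Conclusion.** The point holds as a minor reporting matter. With 10 subjects, uncorrected d is too large on average by 9.4% if divided by the SD of differences, and by about 4% to 9% if divided by the average condition SD, for r from 0 to 0.95. This rests on reading Cohen's d in its usual uncorrected sense, on complete pairs, and on approximate normality with equal SDs.

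The unstated denominator is a missing detail, not an error. It matters because the two candidates can differ by a factor of 0.71 to 3.16 over the same assumed range of r, and a reader cannot tell which one is shown. No p-value, ANOVA result or conclusion from a hypothesis test is affected.

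**What to change.** Replace Cohen's d with Hedges' g in the Statistical Analysis Plan:

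- Name one denominator and use it for every FI and EMG outcome.
- If it is the SD of the differences, multiply d by J(9) = 0.914.
- If it is the average condition SD, use J with df = 2(n − 1)/(1 + r²), with r estimated from the data for that contrast.
- Beside each g, show the raw mean paired difference in outcome units with its 95% confidence interval.

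The choice of denominator is a trade-off for the sponsor: the SD of differences suits planning another crossover, and the average SD expresses the change relative to variation between women.

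The cost is a sentence or two of wording and a short calculation on data already collected. The downside is that reported effect sizes become slightly smaller.
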